3.8 Efficacy Analysis

Efficacy analyses will be performed using the FAS and, where appropriate, the Per-Protocol Set. ORR will be estimated for each cohort evaluated in the Expansion Phase using irRECIST as the primary endpoint. Crude proportion of patients with best overall response of CR or PR, along with a 2-sided 95% CI, will be calculated for each cohort. The width of the CI will be adjusted to account for the multistage design (Atkinson, 1985). Additionally, a 90% one-sided CI of the form $(\pi, 1]$ will be reported for cohort 1 and a 95% one-sided CI will be reported for cohort 4 since the sample size for the Expansion Phases for cohorts 1 and 4 were determined using a one-sided significance level of 10%, 5%, respectively.

Crude proportion of patients with best overall response of CR or PR, along with a 2-sided 92% CI will be calculated for cohorts 2 and 3. ORR based on RECIST 1.1 will be analyzed in a similar manner.

Clinical Benefit Rate

Clinical benefit rate, as determined by irRECIST, will be estimated based on the crude proportion of patients in each cohort whose best overall response during the course of study treatment is a irCR, irPR, or irSD lasting for at least 6 months. Stable disease based on irRECIST will be measured from the start date of study treatment until the criteria for irPD is first met. Approximate 2-sided 95% CIs will be calculated for each cohort. Clinical benefit rate, as determined by RECIST 1.1, will be estimated based on the crude proportion of patients in each cohort whose best response during the course of study treatment is a CR, PR, or SD lasting for at least 6 months. Stable disease based on RECIST 1.1 will be measured from the start date of study treatment until the criteria for PD is first met. Approximate 2-sided 95% CIs will be calculated for each cohort.

Progression-free Survival

The PFS, defined as the number of months from first dose date to PD or death due to any cause, whichever occurs first. Disease assessments will continue until PD, even

after the originally assigned study treatment is discontinued. For purposes of analysis, 1 month is considered 30.4375 days. The duration of PFS as determined by RECIST 1.1 (Eisenhauer 2009) and irRECIST (Seymour 2017) will be summarized descriptively using the Kaplan-Meier method (Kaplan 1958). The PFS at 6 months by irRECIST and RECIST 1.1 will be analyzed in a similar manner.

The date of progression or censoring for PFS will be determined according to the conventions listed in Table 3-1.

All patients are to be followed for disease progression according to the protocol-specified schedule even after a non-protocol, anti-cancer therapy is started. For the primary analysis of PFS, documented disease progression (or death without prior disease progression) occurring after the start of such therapy will be considered as a PFS event.

Table 3-1. Date of Progression or Censoring for Progression-free Survival

Situation	Date of Progression or Censoring	Outcome
Documented disease progression	Date of disease assessment showing documented disease progression	Progressed
Death without documented progression	Date of death	Progressed
No baseline disease assessments	Date of enrollment	Censored
No post-baseline assessment and no death	Date of enrollment	Censored
Alive and without documentation of disease progression	Date of last disease assessment	Censored
Patient lost to follow-up (or withdrew consent from study participation) before documented progression or death	Date of last disease assessment	Censored

Overall Survival

Overall survival is defined as the number of months from first dose date to the date of death (due to any cause). Patients who are alive or lost to follow-up (as of the data analysis cutoff date) will be censored. The censoring date will be determined from the patients' date of last contact or data analysis cutoff date, whichever date occurs first.

The analysis of OS will be based on the methods described above for PFS. The duration of OS will be summarized descriptively using the Kaplan-Meier method with 95% CIs, calculated using Greenwood's formula.

Duration of Response and Time to Response

Duration of response will be calculated for patients who achieve CR or PR. For such patients, DOR is defined as the number of months from the start date of the PR or CR (whichever response occurs first and subsequently confirmed), to the first date that recurrent disease or PD is documented. The same analysis will be repeated for patients who achieve immune-related CR (irCR) or immune-related PR (irPR). The date of progression or censoring for DOR will be determined according to the conventions listed Table 3-2. These conventions are based on the May 2007 FDA Guidance for Industry, '*Clinical Trial Endpoints for the Approval of Cancer Drugs and Biologics*'. DOR will be summarized descriptively using the Kaplan-Meier method.

Table 3-2. Date of Progression or Censoring for Duration of Response

Situation	Date of Progression or Censoring	Outcome
Documented disease progression	Date of disease assessment showing documented disease progression	Progressed
Death without documented progression	Date of death	Progressed
Alive and without documentation of disease progression	Date of last disease assessment	Censored

Time to response will be calculated for patients who achieve a CR or PR. For such patients, TTR is defined as the number of months from the randomization date to the first date the patient achieved a PR or CR (whichever response occurs first and was subsequently confirmed). The same analysis will be repeated for patients who achieve irCR or irPR.

To supplement the above analysis of OS, a summary of the anti-cancer therapies and interventions received following the discontinuation of study treatment, will be provided. Such therapies will be collected during the scheduled post-treatment, follow-

up assessments. The therapies may be classified and summarized as chemotherapy, immunotherapy, radiation, surgery or other.

3.9 Subgroup Analyses

Supportive analyses will be performed to determine whether the estimated treatment effect that is observed for the ORR and PFS (based on irRECIST) is consistent across selected subgroups of patients. The HR (or odds ratio) for treatment effect will be estimated within each subgroup. If a subgroup consists of fewer than 10% of Phase 2 randomized patients, analysis within that subgroup will be omitted. Forest plots will be used to display the ORs (or hazard ratios) and 95% CIs across subgroups.

Subgroup analyses:

- PD-L1 expression (Yes, No, Missing)
- Current Visceral Involvement (Yes, No, Missing)
- Baseline LDH (%>ULN) (Yes, No, Missing)
- Previously treated with ipilimumab and PD-1 (Melanoma cohort only)
- Previously treated with BRAF/MEK Inhibitor (Melanoma cohort only)
- Baseline classical monocytes
- NLR = (ANC/ALC)
- dNLR = (ANC/(WBC-ANC))
- Smoking Status (Current Smoker, Former Smoker, Never a Smoker) (NSCLC Cohorts only)

3.10 Safety Analysis

Safety analyses will be performed on the Safety Analysis Set.

3.10.1 Adverse Events

An AE is defined as any untoward medical occurrence in a patient or clinical

investigation patient administered a pharmaceutical product, and that does not necessarily have a causal relationship with this treatment. An AE can therefore be any unfavorable and unintended sign (including an abnormal laboratory finding), symptom, or disease, temporally associated with the use of a medicinal (investigational) product, whether or not the AE is related to the medicinal (investigational) product. The term also covers laboratory findings or results of other diagnostic procedures that are considered to be clinically relevant as determined by the Investigator.

Analyses of AEs will be based on the principle of treatment emergence. Treatment-emergent AEs are defined as having onset after study drug dosing or a sign, symptom, or diagnosis that worsens after study drug dosing. Henceforth, whenever an analysis or summary of AEs is mentioned, it is intended that this is in reference to TEAEs, unless it is stated otherwise.

If AE start dates are completely missing or partially missing, the date imputation rules described previously in Section 3.1.4 will be applied for the determination of treatment-emergence. This algorithm will be used only if the end date of the AE (if reported) indicates the event was not resolved before the first administration of study drug. Imputed AE dates will not be used to calculate the duration of AE episodes.

All AEs will be coded according to System Organ Class (SOC) and Preferred Term (PT) using the Medical Dictionary for Regulatory Activities (MedDRA) dictionary (Version 18.0 or later).

For the escalation phase, the observed DLT rate in each dose cohort will be calculated by the crude proportion of patients who experienced DLT with a 2-sided, 95% exact binomial CI.

For Phase 1, AE relatedness criteria is defined as “definitely not related”, “probably not related”, “probably related” and “definitely related”.

A summary of AEs, including incidences of:

- AEs
- SAEs
- AEs related to entinostat (“not related”, “unlikely related”, “possibly related”

or “related” for Phase 2)

- AEs related to pembrolizumab (“not related”, “unlikely related”, “possibly related” or “related” for Phase 2)
- AEs related to any study drug
- SAEs related to entinostat, pembrolizumab, or both
- AEs leading to dose modification of entinostat, pembrolizumab, or both
- AEs leading to discontinuation of entinostat, pembrolizumab, or both
- AEs with a fatal outcome
- AEs with a CTCAE severity grade of Grade 3 or greater
- AEs with CTCAE severity of Grade 3 or greater related to entinostat, pembrolizumab, or both

will be presented by dose cohort in Phase 1 and by tumor type in Phase 2.

Incidences of all AEs will be presented by SOC and PT by dose cohort in Phase 1 and by tumor type in Phase 2. SOCs will be sorted alphabetically. Within an SOC, PTs will be presented by decreasing incidence overall. Incidences of SAEs, and incidence of related SAEs by PT only, will be presented by decreasing incidence overall.

Incidence of AEs will also be presented by PT and severity, and by PT and relationship to study drug. Incidence of AEs of Grade 3 or greater, and incidence of related AEs of Grade 3 or greater, will also be presented by PT. For patients experiencing the same PT at multiple severities, the occurrence of the AEs with the greatest severity will be used in the analysis of incidence by severity. For patients experiencing the same PT at multiple relationship levels, the occurrence of the AEs with the strongest relationship to study drug will be used in the analysis of incidence by relationship to study drug.

All reported AEs, regardless of whether they were treatment-emergent, will be included in patient listings. Listings of all SAEs and AEs leading to discontinuation of entinostat, pembrolizumab, or both will also be provided.

3.10.2 Laboratory Evaluations

Hematology and serum chemistries will be summarized using summary statistics for the following values by cohort ~~and overall~~: baseline value, minimum and maximum post-baseline values, average post-baseline value, and last post-baseline value. Change

from baseline for each of these post-baseline values will also be summarized.

Whenever available, laboratory values will be assigned toxicity grades using the NCI-CTCAE, version 4.03. Shifts in laboratory values to outside the local laboratory normal range will be evaluated for selected laboratory tests by assessing, relative to the baseline value, the maximum increase and/or decrease observed throughout the course of study treatment, and the last reported value. The number and proportion of patients with directional shifts above or below the normal range will be summarized for selected laboratory tests. Similar analyses will be performed for shifts in NCI CTCAE toxicity grades relative to the baseline toxicity grade.

Percentages will be based on the total number of patients with a baseline assessment and at least one post-baseline assessment for the given laboratory parameter. Laboratory test groupings and standard normal ranges are described in Appendix 5.1, and CTCAE toxicity grades for hematology and chemistry parameters are described in Appendix 5.2 and Appendix 5.3, respectively.

Listings of all clinical laboratory data for each patient will be provided. A separate listing of all out of normal range as well as all toxicity grade values will also be provided.

3.10.3 Vital Signs

Change from baseline for vital signs (temperature, pulse, systolic/diastolic blood pressure, respiration rate, and weight) will be summarized over time by tumor type.

A patient listing of all vital sign assessments will be provided.

3.10.4 ECG

Electrocardiogram results will be listed and summarized in terms of the number and percentage of patients with abnormal and normal findings, as reported by the Investigator, at the time points where ECGs were assessed (screening and EOT).

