**CONFIDENTIAL**

**SYNDAX PHARMACEUTICALS**

Procedure	Screening (D -21 to -1)	Combination Therapy						EOT 	Safety F/U 	Post- Study F/U
		C1			C2		≥C3			
		D1	D8	D15	D1	D15	Day 1			
Visit Window	-	-	±1D	±1D	±3D	±3D	±3D	±3D	±3D	±5D
Pembrolizumab administration		X			X	\	X			
Blood sample for entinostat pharmacokinetics 		X	X	X	X					
Blood sample for pembrolizumab pharmacokinetics and anti-drug antibodies 		X			X		X		X	
Blood sample for tumor markers 		X			X		X	X		
Pre-treatment/concomitant medications	X	X	X	X	X	X	X	X	X	
Adverse events	X	X	X	X	X	X	X	X	X	
Study drug compliance assessment		X	X	X					X	
Post-study treatment patient contact 										X

 The EOT visit is to be conducted within 7 days of study drug discontinuation.

 The first Safety F/U visit is 30 days after the EOT visit. After completion of the Safety F/U visit, patients who have not experienced PD are to be followed every 2 months until PD and 3 months thereafter until death or closure of the study by the Sponsor.

 The second Safety F/U visit is 90 days after the EOT visit.

 If the screening physical examination was performed within 7 days before baseline (C1D1), then a symptom-directed examination may be performed at baseline.

 An ECG is to be performed during screening, pre-dose on C3D1 and then every 3 cycles thereafter. An ECG may be repeated anytime, as clinically indicated.

 Performed only if last scan was performed >28 days previously.

 Patients will have radiological disease assessments performed during screening and every 6 weeks (+/-3 days) (Week 6, Week 12, etc.) during treatment.

 Performed only if radiological progression was not previously observed on study.

 Disease assessments are to be performed every 6 weeks (+/-3 days) (Week 6, Week 12, etc.) during treatment.

 In addition to screening, thyroid function tests (thyroid-stimulating hormone [TSH, thyrotropin], free thyroxine [T4], and triiodothyronine [T3] or free triiodothyronine [FT3]) are to be performed every 6 weeks during treatment starting at C2.

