#### **9.2.2      Electrocardiograms**

All patients will have a 12-lead ECG performed during screening; pre-dose (i.e., before entinostat and pembrolizumab) on C3D1, and then every 3 cycles thereafter. A 12-lead ECG also is to be performed at the EOT (7 days post-last dose). A 12-lead ECG is to be repeated as clinically indicated.

ECGs will be recorded after the patient has rested in a supine position for at least 10 minutes in each case. The Investigator or designated physician will review the paper copies of each of the timed 12-lead ECGs when they are collected.

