Laboratory values will be assigned toxicity grades when available using the NCI CTCAE. Directional shifts in laboratory toxicity grades (comparing baseline grade with worst post-baseline grade) will be analyzed using standard shift tables, presenting number and proportion of patients and their maximum grade shift. For analytes without a toxicity grading scale, the shift table will present directional shifts from baseline to above or below the laboratory standard normal range using the maximum increase and/or decrease observed throughout the course of treatment/observation.

Vital signs will be summarized in a descriptive manner by calculating the mean, standard deviation, median, and range in the same manner described for laboratory values. The Wilcoxon signed rank test may be used to assist in the identification of any systematic changes.

ECG results will be listed and summarized in terms of the number and percentage of patients with abnormal and normal findings, as reported by the Investigator, at the time points assessed (screening and EOT).

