2.3.2 Estimated Treatment and Study Duration

The maximum duration of treatment for this study is planned to be 35 cycles (approximately 2 years.)

Patients who complete C1 may continue on study as long as, in the Investigator's judgment, the patient is tolerating the study treatment, is not at an increased safety risk, and continues to meet protocol eligibility criteria.

If a patient permanently discontinues 1 of the 2 study drugs (either entinostat or pembrolizumab), the patient may continue to receive monotherapy for up to 2 years, unless alternate therapy is started or another discontinuation criterion is met (Section 10 of the protocol).

Patients who discontinue both study drugs will receive standard of care outside the auspices of this study at the Investigator's discretion.

After discontinuation of both study drugs, patients will complete an EOT visit within 7 days (+/- 3 days) after the last study drug dose and Safety Follow-up visits 30 days (+/- 3 days) and 90 days (+/- 3 days) thereafter. After completion of the 30-day Safety F/U visit, patients who have not experienced PD are to be followed every 2 months until PD and every 3 months thereafter until death or closure of the study by the

Sponsor. The purpose of the post-treatment follow-up is to ascertain the duration of PFS for all patients in the study. After development of PD, surviving patients are to be followed on an every 3-month basis for alternate therapy and survival until closure of the study. Up to approximately 40 study centers are planned to be recruited for participation in this study.

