3.3.3 Safety Variables

Safety variables include:

- Determination of DLT, MTD and RP2D
- Incidence of TEAEs:

TEAEs are defined as any AE occurring or worsening in severity after the administration of study drug. TEAEs will be categorized as:

- Relationship to entinostat
- Relationship to pembrolizumab
- Severity/Grade according to National Cancer Institute Terminology Criteria for Adverse Events (NCI CTCAE) Version 4.03
- Action with respect to entinostat
- Action with respect to pembrolizumab
- Seriousness and outcome
- Change in chemistry and hematology parameters from baseline to minimum and maximum post-baseline values, average post-baseline value, and last post-baseline value
- Shifts in chemistry and hematology parameters from baseline to worst post-baseline in CTCAE toxicity grade
- Shifts in chemistry and hematology parameters outside the laboratory normal range from baseline to maximum increase and/or decrease, and last post-baseline value
- Change from baseline in vital signs and weight at each post-baseline time point
- Change from baseline in 12-lead ECG parameters at each post-baseline time point
- Change from baseline in ECOG at each post-baseline time point

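### The ECG analysis text names screening and end of treatment as the only time points, so the ECG summary as written omits every scheduled on-treatment ECG and conflicts with the protocol schedule and SAP 3.3.3

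*SAP*

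**What the plan says.** **Analysis text.** SAP 3.10.4 lists ECG results and counts patients by the investigator's normal or abnormal reading "at the time points where ECGs were assessed (screening and EOT"). Protocol 12.4.7 sets the same limit: "at the time points assessed (screening and EOT").

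**Schedule.** Protocol 9.2.2 requires a 12-lead ECG for all patients at screening and again "pre-dose (i.e., before entinostat and pembrolizumab) on C3D1, and then every 3 cycles thereafter". It adds a further one: "A 12-lead ECG also is to be performed at the EOT (7 days post-last dose"). Footnote 5 to Table 1-1 gives the on-treatment schedule in the same terms, "An ECG is to be performed during screening, pre-dose on C3D1 and then every 3 cycles thereafter", and Table 1-2 for the EMIC cohort has the same footnote.

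**Endpoint and variable.** Protocol 3.2 and SAP 2.2.2 both include change from baseline in ECG among the safety endpoints. SAP 3.3.3 is more specific: "Change from baseline in 12-lead ECG parameters at each post-baseline time point".

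**Planned outputs.** SAP 6.1 lists one ECG table, 14.3.16, on ECG normality by assessment; its title is cut off in the text available. SAP 6.3 lists Listing 16.2.3.13 for 12-lead ECGs. No listed table covers change in ECG parameters.

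**The concern.** The parenthesis in SAP 3.10.4 and Protocol 12.4.7 does not match when ECGs are recorded. Read as a description, it is wrong. Read as an instruction to the programmer, it removes every scheduled ECG taken between the first dose and the end-of-treatment (EOT) visit.

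ECG change is a stated safety endpoint, and each cohort is a single arm, so within-patient change during treatment is the main ECG evidence the study can give. A reading that becomes abnormal during treatment and is normal again by EOT would not be counted in the ECG summary.

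The other safety data are handled more fully. SAP 3.10.2 gives laboratory values minimum, maximum, average and last post-baseline summaries with shifts, and SAP 3.10.3 summarises change in vital signs over time. The documents give no reason for treating ECGs differently.

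**Working it through.** The plan gives no figure to reproduce. The check compares the texts and then counts the ECGs affected.

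**Texts side by side**

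| Source | ECG time points |
|---|---|
| Protocol 9.2.2 | Screening, C3D1, every 3 cycles after that, EOT |
| Tables 1-1 and 1-2, footnote 5 | Screening, C3D1, every 3 cycles after that |
| SAP 3.3.3 | Each post-baseline time point (change from baseline) |
| SAP 2.3.8 | Screening and as clinically indicated, with a reference to the schedule |
| Protocol 12.4.7 | Screening and EOT |
| SAP 3.10.4 | Screening and EOT |

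The two analysis sections agree with each other and disagree with the schedule. SAP 3.3.3 agrees with the schedule, but SAP 3.10.4 gives no method for its variable and SAP 6.1 lists no table for it.

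**Count of ECGs affected**

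- Maximum treatment length, SAP 2.3.2: "The maximum duration of treatment for this study is planned to be 35 cycles".
- On-treatment ECGs fall at C3, C6, ..., C33, because the next (C36) lies beyond cycle 35. Number = (33 − 3)/3 + 1 = 11.
- Scheduled time points for a patient treated for all 35 cycles = 1 (screening) + 11 (on treatment) + 1 (EOT) = 13.
- Summarised as written: 2 of 13. Of the 12 post-baseline time points, 1 is summarised.

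For a patient who starts *c* cycles and attends day 1 of each, the number omitted is *c*/3 rounded down:

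| Cycles started | Scheduled on-treatment ECGs omitted |
|---|---|
| 1–2 | 0 |
| 3–5 | 1 |
| 6–8 | 2 |
| 9–11 | 3 |
| 33–35 | 11 |

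The documents give no expected treatment duration, so the average number omitted cannot be derived. The range is 0 to 11 per patient.

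**The case against.** **Clinically relevant findings are tabulated elsewhere.** A reader might infer that an ECG abnormality arising on treatment and resolving by EOT reaches no summary table at all. The documents do not support that. Under Protocol 9.2.2 a physician reviews each ECG when it is collected, and the adverse event definition in SAP 3.10.1 takes in diagnostic results that the investigator considers clinically relevant. Such a finding enters the treatment-emergent event tables by preferred term, severity and relationship, and the treatment-modification tables if dosing changed. All ECGs also go into Listing 16.2.3.13. This objection stands and limits the harm. It does not supply rates of abnormal ECGs by visit, because a listing gives no rates and findings not judged clinically relevant are not adverse events.

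**The restriction may be only a drafting slip.** The main clause of SAP 3.10.4 refers to the time points at which ECGs were assessed, SAP 3.3.3 covers all post-baseline time points, and the title of Table 14.3.16 would fit a by-visit table. A programmer might therefore produce the full table. That is possible, but the governing sentence then names two visits, and the SAP should not depend on its being ignored.

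**The count is a ceiling.** Eleven applies only to a patient still on treatment at C33. This is correct, and the count is stated here as a maximum.

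**Numeric ECG data may not exist.** Protocol 9.2.2 describes review of paper copies, and both analysis sections describe a normal or abnormal reading. The documents available do not show that intervals such as QTc are entered in the eCRF. A reader might infer that the change-from-baseline table could simply be run from data in hand; that is not established.

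**No specific cardiac signal is cited.** The QTc limit of 470 msec is an eligibility criterion. It does not show that a QT effect is expected, and the point does not rely on one.

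**Conclusion.** The time points in SAP 3.10.4 and Protocol 12.4.7 are wrong against the protocol's own schedule and conflict with SAP 3.3.3. Followed as written, the normal/abnormal summary covers 2 of up to 13 scheduled time points and omits between 0 and 11 on-treatment ECGs per patient, depending on time on treatment. What is lost is the tabulated rate of abnormal ECGs at on-treatment visits; the ECGs themselves and the reporting of clinically relevant events are not lost.

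This assumes that the parenthesis governs Table 14.3.16, whose full title is not visible, and that the on-treatment ECGs follow the schedule from C3D1 to the 35-cycle limit.

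The correction should be made because ECG change is a stated safety endpoint. The safety analysis is descriptive, and the response-rate criteria for the cohorts do not depend on it.

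**What to change.** 1. In SAP 3.10.4 and Protocol 12.4.7, replace the parenthesis with all scheduled time points (screening, C3D1, every 3 cycles after that, EOT) for the investigator-reported normal/abnormal summary. Make the title and shell of Table 14.3.16 match.
2. Reconcile SAP 3.3.3 with 3.10.4. First check whether numeric ECG parameters are in the eCRF. If they are, add a change-from-baseline table by time point to SAP 3.10.4 and SAP 6.1. If they are not, remove the variable from 3.3.3 and say that the ECG endpoint is addressed through the normal/abnormal readings.
3. Optionally, add a table of baseline versus worst post-baseline reading (normal or abnormal) from the same data, stating whether unscheduled ECGs count. Neither document promises this table.

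**Cost.** Items 1 and 3 use ECGs the protocol already requires and need no new visit or procedure: a wording change in two documents, more rows in one table, and one small extra table if item 3 is adopted. Item 2 costs one further table or one deleted line, depending on what the eCRF holds.
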